The appearance of mood and behavioral symptoms during pregnancy and the postpartum period has been extensively reported. While there has been much speculation about possible biologically based etiologies for postpartum disorders (PPD), none has ever been confirmed. Preliminary results from two related studies (protocols 90-M-0088, 92-M-0174) provide evidence that women with menstrual cycle related mood disorder, but not controls, experience mood disturbances during exogenous replacement of physiologic levels of gonadal steroids. The present protocol is designed to create a “scaled-down” hormonal milieu of pregnancy and the puerperium in order to determine whether women who have had a previous episode of postpartum major affective episode will experience differential mood and behavioral effects compared with controls and to determine whether it is the abrupt withdrawal of gonadal steroids or the prolonged exposure to gonadal steroids that is associated with mood symptoms. Supraphysiologic plasma levels of gonadal steroids will be established, maintained, and then rapidly reduced, simulating the hormonal events that occur during pregnancy and parturition. This will be accomplished by administering estradiol and progesterone to women who are pretreated with a gonadotropin releasing hormone (GnRH) agonist (Lupron). After eight weeks, administration of gonadal steroids will be stopped in one group of patients and controls, and a sudden decline in the plasma hormone levels will be precipitated. Another group will be maintained on supraphysiologic levels of estradiol and progesterone for an additional month. Outcome measures will include mood, behavioral, and hormonal parameters.

## 1. Introduction:

### a. Background and Introduction

Affective syndromes that occur during the postpartum period have traditionally been divided into three categories: 1) postpartum “blues”, 2) postpartum depression, 3) puerperal psychosis. The present protocol will only deal with the last two categories, which are associated with more persistent symptoms and with a higher rate of morbidity.

Puerperal psychosis is the most severe form of psychiatric disturbance in the puerperium. This condition is characterized by extreme agitation and confusion, lability of mood, severe sleep disturbances, possible paranoid or grandiose delusions, and in some cases prominent hallucinations. Results of both retrospective case register studies and longitudinal prospective studies have observed that the majority of cases of puerperal psychosis begin during the first few weeks after parturition (1,2). The prevalence of psychosis in the month after childbirth is approximately 22 times that of any month in the preceding two years (3). Women with a history of bipolar or schizoaffective illness are particularly at risk, and about 50% of these women relapse in the first few months after delivery (4-6). In fact most cases of postpartum psychosis are considered to be an extreme manifestation of a bipolar disorder (7), and the overall incidence of this condition is very low, occurring in 0.2% of all deliveries.

Postpartum depression is clinically similar to the DSM-IV defined major depression, but its onset has a temporal relationship to parturition. The main symptoms are appetite and sleep disturbance, excessive fatigue, sadness and anhedonia, excessive guilt, psychomotor and cognitive disturbances and suicidal ideation. The two to three month prevalence rates of postpartum depression in studies using conventional diagnostic criteria (8) (e.g., RDC, DSM-III) have been reported to be in the range of 8.2% to 14.9% (9,10). Some studies (1,10,11), but not

all (12), have reported that the incidence of depression is increased significantly during the first 3 months after birth as compared to during pre-pregnancy, pregnancy or the period after the first postpartum year. Others have disputed this association, arguing that the prevalence of depression during the postpartum period is no greater than that for depression at other periods of a woman's life (12). Factors associated with postpartum depression are a history of psychiatric illness, family history of psychiatric illness, marital disharmony and lack of confiding relationships, maternal age and the number of life events in the previous year (13-15). Additionally, several studies have suggested that a past history of postpartum disorders (PPD) may predispose women to develop an episode of PPD during subsequent pregnancies. In a longitudinal prospective study (16) women with a past history of PPD had a significantly higher rate of PPD during a subsequent pregnancy than women without a history of PPD, specifically, 28-40% compared with 10%. These findings are corroborated by preliminary results from a longitudinal prospective study conducted at the Massachusetts General Hospital suggesting a higher relative risk of PPD during subsequent pregnancies in women with a prior episode of PPD (17,18).

**b. Biological Factors in Postpartum Disorders:**

Hormonal factors have been implicated as having an important etiological role in the development of PPD. Pregnancy is accompanied by a slow but sustained rise in various steroid and peptide hormones, followed by a sudden drop over the first few days after delivery. During the third trimester of pregnancy, plasma progesterone levels are approximately 150 ng/ml and estradiol reaches plasma levels of approximately 10-15 ng/ml. These levels represent a 10 and 50 fold increase, respectively, of maximum menstrual cycle levels (19). After parturition progesterone and estradiol levels drop to early follicular phase levels within days (20).

A role for progesterone and estradiol in postpartum mood disorders is suggested by their manifold neuroregulatory effects (21).

1). Progesterone - In addition to its genomic effect, progesterone has rapid effects on neuronal membranes (22). The rapid membrane action of progesterone metabolites is thought to be responsible for the anaesthetic action of progesterone (23) and occurs through positive modulation of the gamma-aminobutyric acid-A (GABA-A) receptor (24). These progesterone metabolites (e.g., allopregnanolone) may be formed from circulating progesterone or may be synthesized de novo in the brain and are, therefore, known as neurosteroids. Some researchers have postulated that the levels of neurosteroids reached in the brain are physiologically significant and compatible with their playing a neuromodulatory role during the estrous cycle and pregnancy, possibly associated with behavioral changes seen in these conditions (25,26). Studies, using different outcome measures, confirm that in female rats, GABA-A receptor sensitivity to specific neurosteroids such as allopregnanolone (26) is cycle-dependent. Pregnancy and the postpartum period have also been reported to both increase and decrease the affinity of GABA receptors in the brain for a variety of ligands (26,27). These effects of progesterone could provide the theoretical ground for a “progesterone withdrawal” hypothesis for PPD.

Studies have been unable to identify a significant association between progesterone levels and either the “blues” (28,29) or postpartum depression (30). However, one study did report a significant correlation between progesterone levels around parturition and the “blues.” Additionally, Dalton treated women at risk for the development of PPD with open label progesterone following parturition and observed no recurrence of PPD (31), suggesting a preventive effect of progesterone on the onset of PPD in this sample. In contrast, there is at least one study that indicates that giving progestins during the postpartum period actually increases

postpartum depressive symptoms (32). It remains unclear whether there is a causal role for changing levels of progesterone in the onset of symptoms of PPD (30).

2). Estradiol - Estradiol has been found to alter brain neurotransmitter activity in several ways: in the hypothalamus, estradiol (E2) is associated with decreased norepinephrine synthesis and increased choline acetyltransferase activity (33), decreased glutamic acid decarboxylase activity (34), and increased muscarinic receptors (35,36); in the cerebral cortex, E2 replacement in ovariectomized rats decreases beta-adrenergic and 5HT-1 receptors but increases 5HT-2 receptors (37); and E2 facilitates excitability of hippocampal neurons in vitro (38,39) and in vivo (40), through both short term and long term mechanisms, and decreases the threshold to electrically-induced seizures in the medial amygdaloid nucleus (41,42). Additionally, E2 increases NMDA binding sites in the CA1 region of the hippocampus (43). An anti-dopaminergic effect of estradiol at both the pituitary and striatum has been described (44). Elevated levels of estradiol have been reported to decrease tyrosine hydroxylase activity and hence dopamine synthesis (45), while even low doses can modulate the striatal agonist affinity states of the D2 receptor (46). Consistent with these putative antidopaminergic effects is the observation of improvement of L-DOPA-induced tardive dyskinesia with estradiol (47) and the amelioration of psychotic symptoms in schizophrenic women during the high estradiol phase of their menstrual cycle (48). Conversely, it should be noted that enhanced dopamine receptor sensitivity following estradiol administration has been reported (49,50). Regional brain MAO activity has been shown to be increased by progesterone (51) and decreased by estradiol (52).

Most studies have failed to show an association between blues or depression and estradiol plasma levels around parturition (29,30). However, there are preliminary data that indirectly suggest a role for estradiol in postpartum disorders. Women who later have a recurrence of PPD, as opposed to women who remain well, show an increased D2 sensitivity postpartum as reflected

by exaggerated growth hormone response to apomorphine (6,53). This modification in D2 sensitivity may result from altered effects of estradiol on D2 receptors in women with PPD, given the ability under normal conditions of E2 to inhibit D2 activity by uncoupling the D2 receptor from its second messengers and to decrease D2 receptor sensitivity (46,54). Furthermore, estradiol replacement has been reported to be an effective treatment for postpartum depression under double-blind, placebo-controlled conditions (55).

3) Other hormones - A significant association has been found between postpartum thyroid dysfunction and the development of postpartum depression (56,57). It has also been shown that women with a positive thyroid antibody status, which occurs in approximately 10% of normal women, are prone to episodes of postpartum depression (58), and up to 1% of all postpartum women may develop a depression associated with autoimmune thyroid disease. More recently, Pedersen et al., in press, reported a negative correlation between antenatal thyroxine levels and self-reported depression scores in the postpartum period, suggesting that low antenatal thyroid status is a risk for developing PPD.

Preliminary studies also indicate a possible association of HPA axis dysregulation and the development of postpartum depression. There is one study suggesting that symptoms of depression during pregnancy are associated with lower levels of CRH (59). Our own preliminary data indicate a significant study phase effect on integrated cortisol secretion (increased during addback compared with the withdrawal phase) and a trend for a diagnosis by hormone condition interaction, reflecting increased cortisol in women with a history of PPD compared to controls during the addback phase (60).

Other hormones such as prolactin, androgens, beta-endorphin, vasopressin, oxytocin, and growth hormone have marked fluctuations during pregnancy and parturition. Association between these hormones and psychiatric symptoms have not been substantiated.

Despite these observations, there are only a few systematic studies of the role of gonadal steroids in the etiology of PPD. This probably reflects a number of factors, including the low prevalence of PPD in the community, the presence of numerous psychosocial and medical stressors during pregnancy and the puerperium, and the difficulties involved in recruiting and evaluating women who are either pregnant or lactating and nursing an offspring. To avoid these problems, we propose to study women with a history of PPD compared with women without a history of PPD, in order to answer the questions, 1) “Are women who develop PPD specifically susceptible to the hormonal events of pregnancy and the puerperium?”; and 2) Is it the abrupt withdrawal of gonadal steroids or the prolonged exposure to gonadal steroids that is associated with mood symptoms in these women?

Preliminary results of this study demonstrate that acute withdrawal of estradiol and progesterone is associated with a recurrence of mood and behavioral symptoms in women with a history of PPD but not in women lacking such history (61). These findings document a differential sensitivity to changes in gonadal steroid levels in women with a history of PPD, similar to what is seen in women with premenstrual syndrome. However the specific role of hormonal withdrawal is unclear as we observed that women with PPD were also significantly more symptomatic than controls during the addback phase of hormonal treatment (though less robustly than during the withdrawal phase). It is possible, therefore, that the duration of exposure to gonadal steroids rather than their withdrawal was the critical determinant of symptom precipitation; i.e., continued exposure to estradiol and progesterone replacement in our study might have been associated with equal levels of mood symptoms. Accordingly, we propose to mimic the hormonal events of pregnancy by randomly assigning patients and volunteers to either a withdrawal or continued replacement group (details in Clinical Assessment and Procedures). Furthermore, in order to establish PPD as a distinct phenotype, we will study a

group of women with histories of major depression occurring outside of the perinatal period to test whether the mood and HPA axis effect of this paradigm are specific to postpartum depression or a nonspecific response to any major depressive episode.

Certain forms of affective illness are distinguished by their appearance during periods of reproductive endocrine change, such as during pregnancy and the postpartum/puerperium. Unlike depression accompanying endocrinopathies (e.g., hypothyroidism), these peripartum mood disorders have been shown in our prior work to represent differential sensitivity to an otherwise normal reproductive endocrine stimulus (62). As such, these disorders offer a unique opportunity to identify underlying mechanisms of affective dysregulation: i.e., in this protocol we have identified the trigger, but the underlying susceptibility that transforms a normal endocrine signal into an abnormal response is undetermined. One approach we have undertaken is to study women with a history of peripartum mood disorders (PPMD) to determine whether blinded exposure to supraphysiologic levels of reproductive steroids will result in abnormal neural network activation in affective regulating and reward circuitries. These studies, will not, however, explain the underlying cellular/neural differences that transform a normal signal into an abnormal response. For that purpose, we propose to opportunistically collect blood samples from women already diagnosed with PPMD in order to generate human induced-pluripotent cells (iPSCs), neural progenitors, and possibly human induced serotonergic and dopaminergic neurons for transcriptomic analysis that can be compared with those from controls under baseline conditions and following stimulation with ovarian steroids (i.e., estradiol and progesterone). This strategy has been successfully employed by our group in a related disorder, premenstrual dysphoric disorder (PMDD), albeit with lymphoblastoid cell cultures (LCLs) rather than h-iPSCs. h-iPSCs/neural progenitors offer the advantage of being a neural tissue and, therefore, physiologically more relevant to these conditions than the immune tissue represented by the

LCLs. Given, however, observation of immune dysfunction in women with postpartum depression (women with PPD have a higher than expected rate of postpartum thyroiditis), we will also create LCLs to determine the following: 1) whether clear differences in genomic expression can be identified that may explain the observed relationship between immune dysregulation and PPD; and 2) whether the differential transcriptional responses to ovarian steroids observed in women with a history of PMDD – a putative biomarker of hormone sensitivity – can be observed in women with a different disorder (PPD), albeit one characterized by susceptibility to reproductive hormone-induced affective dysregulation.

Cellular models, involving neuronal cells, lymphoblastoid cell lines (LCLs), and more recently neural progenitor cells (63) have many advantages, but also distinct limitations for the study of brain diseases (64), (65), (66). Studies employing both LCLs and neural progenitor cells have been employed to investigate several forms of both inherited diseases (67), (68) and neuropsychiatric conditions (69), (64), (70), (71), (72). Despite limitations of peripheral blood cell-derived cell lines, these cellular models offer the opportunity to identify biochemical characteristics related to specific disease phenotypes. Additionally, recent evidence supports the use of LCLs for identifying both local and long-distance regulatory elements involved in immune-mediated disease states (73).

## 2: Specific Aims

Aim 1: Determine whether cellular substrates of differential hormone sensitivity can be identified through creating neuronal progenitors exposed to high dose estradiol (E) and progesterone (P) (100nm each x 3 days) and withdrawal (3 days), with transcriptomic analyses conducted after each treatment.

Aim 2: a) Determine whether transcriptional response in immune-relevant pathways to hormone response and withdrawal in LCLs will, in these long term cultured cells, distinguish women with PPD from controls and, therefore, further implicate differential immune responses in the pathophysiology of PPD; and b) replicate differences in the polycomb repressor complex under both basal and E- and P-stimulated conditions that we previously observed in premenstrual dysphoric disorder (PMDD).

Hypotheses: H1) After exposure to combined E and P, neural progenitor cells from women with PPD will reveal a transcriptional pattern that differs from that in controls; H2) Similar to PMDD, LCLs from women with PPD will demonstrate a differential basal and hormone-stimulated transcriptional response in network and pathways analyses(e.g., Weighted Genome Correlation Network Analysis (WGCNA), Gene Set Enrichment Analysis (GSEA), and Database for Annotation, Visualization and Integrated Discovery (DAVID)).

Experimental Plan: This component of our protocol will build on access to unique samples of women with peripartum mood disorders as follows: 1) to create human-induced pluripotent cells (h-iPSCs) and neuronal progenitor cells whose transcriptional responses to ovarian steroids in vitro will be assessed; and 2) to create lymphoblastoid cell lines (LCLs).

Participants: PPD- Peripheral blood samples will be obtained from women with PPD and control women (matched for age, race and parity) who met the following criteria: 1) participated in the GnRH agonist and E/P replacement-then-withdrawal paradigms conducted at the NIMH IRP; and 2) clearly demonstrated recurrence of depression (in the women with past PPD but not controls) after E/P withdrawal. This group of women with past PPD and controls therefore will represent a highly selected phenotype in which we have demonstrated behavioral ovarian steroid

sensitivity (in past PPD) or the absence of this phenotype (in controls). All women will be otherwise healthy, and medication free.

h-iPSCs: h-iPSCs will be generated from Sendai virus-transformed T cells (74), a procedure already successfully accomplished in the LNG laboratory, and then differentiated to neuroprogenitor cells (75) (also successfully achieved by LNG), serotonergic (76) (experiments underway in LNG) and dopaminergic neurons (77), (69). Following differentiation, cells will be cultured in a sex steroid-free growth medium which is phenol red-free media to reduce possible exposure to steroid-like activity prior to experimental exposure.

LCLs: EBV-transformed lymphoblastoid cell lines will be made from peripheral blood as described previously (78), and cells from women with PPD and matched controls will be cultured under identical conditions. As for IPSCs, 5 days before hormone exposure, LCLs will be cultured in a sex steroid-free growth medium of phenol red-free media supplemented with 15% knock out serum (KOSR) (estrogen-depleted).

PPD and control cells will be cultured and collected at baseline, after exposure to combined E/P at supraphysiologic doses of 100nm each (in DMSO) for 3 days, and after withdrawal to vehicle only (DMSO alone) or continued E/P treatment for 3 days (to control for latency following initial hormone exposure).

RNA sequencing: Total RNA will be isolated from the cell pellets and then treated with DNase to remove any traces of genomic DNA contamination. Quality assessment of the RNA is done by an Agilent® 2100 Bioanalyzer. Whole-transcriptome RNA sequencing will be performed using an Ion Torrent NGS Sequencer, the Ion Proton. Total RNA will be polyAAA selected and used to prepare cDNA libraries using the Ion Total RNA-Seq Kit v2, barcoded with Ion Xpress™ RNA-Seq Barcodes.

Analysis of RNA sequencing data: Reads will be mapped to reference genome Hg19 and normalized. Using edgeR analyses (or other similar platforms), performed in either CLC Bio Workbench 11 or “R” programming environment (or other appropriate environment), differentially expressed genes will be computed between conditions and multiple comparisons will be corrected using the False Discovery Rate (FDR, Benjamini Hochberg) method. For each gene of interest, normalized expression between untreated and hormone treated/withdrawn cell cultures will be further analyzed by 2-way ANOVAs, with hormone condition (i.e., untreated, hormone exposure, hormone withdrawal) as the within-groups factor and diagnostic group (i.e., PPP or PPD versus Controls) as the between-groups factor. The appropriate post-hoc tests will be performed should significant interactions be detected.

Pathway/Network analysis of RNA sequencing data: Pathway/Network analyses (e.g., Gene Set Enrichment Analysis (GSEA)) will be performed on differentially expressed genes to identify significant biological processes, molecular functions and cellular components for samples in the baseline (untreated), E/P-treated condition, and after withdrawal. Additional analyses that could be performed include WGCNA to examine modules of differentially expressed genes between cells from women with PPD and controls under each hormone condition. Finally, we will subject all differentially expressed genes to other bioinformatics tools, such as the Database for Annotation, Visualization and Integrated Discovery (DAVID) to identify functionally related groups and networks, which can help to detect impacted biological, molecular and cellular functional domains.

Validation of RNA-sequencing: mRNA expression analysis using qRT-PCR will be used to quantitate differentially expressed genes at baseline, after E/P exposure, and after E/P withdrawal. TaqMan qRT-PCR assays will be carried out according to the assay developer’s

recommended conditions on a 7900HT Fast Real-Time PCR System. A two-tailed, unpaired Students t-test will be performed for each comparison.

Additional Analyses: it is possible that whole exome sequencing will be performed in these samples, and evaluations of the methylome will be performed on repeated DNA samples across each of the hormonal conditions established in the clinical protocol (i.e., baseline, add-back, withdrawal and follow-up).

This study will be done in collaboration with [name] at the NIAAA.

c. Medications Employed in this Study:

In order to avoid fluctuating hormonal levels with subsequent menstruation, and to ensure reduction of gonadal steroids to hypogonadal levels during the withdrawal phase, suppression of ovarian function will be induced with the GnRH agonist leuprolide acetate (Lupron). As described in detail in protocol # 90-M-0088, Lupron is a synthetic nonapeptide that functions as an agonist that is 80 to 100 times more potent than natural GnRH in inducing the release of LH (79). During the first week of Lupron therapy, there is an initial increase in the pituitary release of LH and FSH leading to a transient increase in levels of the gonadal steroids estrone and estradiol in premenopausal females. However, within two to four weeks after initiation of treatment, there is a subsequent decrease in the number of GnRH receptors and an inhibition of pituitary elaboration of gonadotropins, leading to levels of estradiol similar to those observed in post-menopausal women.

Following suppression with Lupron, estradiol and progesterone will be administered in oral micronized form. The administration of 17 beta estradiol via an oral route using micronized E2 was chosen for this study because it has several advantages. First, it delivers the primary ovarian estradiol, into the circulation at a rate resulting in sustained levels of estradiol and

constant rates of excretion of estradiol conjugates (80). Second, at doses of 3-6 mg/day, it delivers sufficient estradiol into the circulation to raise estradiol plasma concentrations to levels similar to those of women around the ovulation phase of their menstrual cycle (80), levels that while far from reaching full pregnancy levels would give sustained supraphysiologic estradiol levels compatible with early pregnancy. Third, micronized estradiol has a short half-life, thus facilitating rapid reduction in plasma levels. Finally, the dose can be easily adjusted so that the presence of minor side effects such as nausea may not require complete cessation of the medication.

Orally administered micronized progesterone is biologically active and at doses of 600-1600 mg/day will result in plasma levels of 30-40 ng/ml (81,82). Progesterone in suppository form has been approved by the IRB for administration to patients with menstrual related mood disorders (MRMD) and controls under NIMH protocols # 92-M-0174, 90-M-0088.

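### In the cell experiments, hormone exposure is compared with an untreated baseline and no parallel DMSO-only culture, so the exposure effect cannot be separated from vehicle and three days in culture

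*Combined protocol and SAP*

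**What the plan says.** The cell component is described in section 1 of the protocol, under 2: Specific Aims. The paragraph after the LCL description sets out the collections. Cells are "cultured and collected at baseline, after exposure to combined E/P at supraphysiologic doses of 100nm each (in DMSO) for 3 days", and then a second time "after withdrawal to vehicle only (DMSO alone) or continued E/P treatment for 3 days (to control for latency following initial hormone exposure". That makes four conditions: baseline, three days of E/P, three further days of DMSO alone, and three further days of E/P.

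The paragraph on analysis of the RNA sequencing data specifies a two-way ANOVA "with hormone condition (i.e., untreated, hormone exposure, hormone withdrawal) as the within-groups factor". The continued-E/P culture is not a level of that factor. The second factor is diagnosis, which varies between lines. The pathway paragraph describes results "for samples in the baseline (untreated), E/P-treated condition, and after withdrawal", and the validation paragraph uses qRT-PCR to "quantitate differentially expressed genes at baseline, after E/P exposure, and after E/P withdrawal". All three analyses use the same three conditions, and the reference is untreated.

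**The concern.** The plan treats vehicle and elapsed time as worth controlling. It names DMSO as the solvent, withdraws cells to DMSO rather than to plain medium, and adds continued E/P to handle latency. All of this applies to the second three-day period only. In the first period, where the response to hormone is measured, nothing plays the same part.

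Two results are at stake:

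- **Genes called hormone-responsive.** Differential expression is computed between conditions and the resulting genes go to pathway analysis. A gene that moves with solvent or with time in culture enters that list as a hormone gene. Benjamini-Hochberg correction does not remove it, because the shift is real and only its cause is misassigned. qRT-PCR on the same three conditions would confirm the shift without identifying its cause.
- **Differential hormone sensitivity, the subject of Aim 1.** A diagnosis-by-exposure interaction can be read that way only if PPD and control lines respond alike to DMSO and to three days of culture. The planned conditions cannot test this.

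**Working it through.** The documents give no sample size, power or alpha for the cell experiments, so there is no planned figure to reproduce. The question is which effects the listed conditions can separate.

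**Step 1. Code the conditions.** Let D be the effect of DMSO, T1 that of culture days 0-3, T2 that of days 3-6, H the three-day hormone effect, W the residue of past exposure after withdrawal, and C the extra effect of continuing E/P to day 6. The expected expression of a gene is then:

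| Condition | Expected value | In the ANOVA? |
|---|---|---|
| Untreated baseline | mu | yes |
| E/P, 3 days | mu + D + T1 + H | yes |
| Withdrawal to DMSO, 3 more days | mu + D + T1 + T2 + W | yes |
| Continued E/P, 3 more days | mu + D + T1 + T2 + H + C | no |
| *DMSO only, 3 days (not planned)* | mu + D + T1 | no |

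The first row is an inference. The text says baseline and untreated, listed before exposure. It does not say day 0 or state that DMSO is absent.

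**Step 2. Form the contrasts.**

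- Exposure minus untreated = D + T1 + H.
- Continued E/P minus withdrawal = H + C - W. Vehicle and time cancel, but this compares staying on hormone with coming off it. It is not H.
- Withdrawal minus untreated = D + T1 + T2 + W.
- Exposure minus DMSO only at day 3 = H.

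**Step 3. Is H estimable?** H is estimable if its coefficient vector lies in the row space of the conditions.

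| Conditions used | Rank | H estimable |
|---|---|---|
| Three ANOVA levels | 3 | no |
| All four collected | 4 | no |
| Four, with a never-exposed DMSO culture added at day 6 only | 5 | no |
| Four, with DMSO only at day 3 added | 5 | yes |
| Four, with DMSO only at day 3 replacing the untreated baseline | 4 | yes |

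The four planned conditions yield H only under added assumptions: a linear time effect, the same hormone effect at days 3 and 6, and W = 0. The last cannot simply be assumed, because a withdrawal effect is what the experiment sets out to look for.

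**Step 4. Group by exposure.** The PPD-minus-control difference in (exposure minus untreated) is (difference in H) + (difference in D + T1). It equals the hormone difference only if D and T1 are the same in both groups. With a day-3 DMSO culture in both groups it is estimable without that condition.

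**Step 5. Illustrative size.** Take a gene with H = 0 and a vehicle/time shift of d standard deviations of the within-line difference, tested with a two-sided paired t test at p<0.001 (nominal rate 0.1%). With n lines, the flag rate is the probability that a non-central t with n - 1 degrees of freedom and non-centrality d times the square root of n exceeds the critical value in absolute size. The critical values are 8.61, 4.78 and 3.88 for n = 5, 10 and 20.

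| Assumed shift d | 5 lines | 10 lines | 20 lines |
|---|---|---|---|
| 1 SD | 1.7% | 16% | 71% |
| 0.5 SD | 0.4% | 1.7% | 8.7% |
| 0.25 SD | 0.16% | 0.36% | 1.0% |

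The values of d and n are assumptions, and p<0.001 stands in for the plan's false-discovery-rate rule.

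**The case against.** The strongest reply is that the study's question is about diagnosis, and there the problem largely cancels. PPD and control LCLs are to be cultured under identical conditions, so vehicle and time effects common to both groups drop out of the interaction. H1 compares the groups after exposure and needs no untreated reference. The basal parts of H2 and Aim 2b compare groups at one condition and are not touched. All of this stands. A reader might infer that every aim and hypothesis of the cell component fails; the documents do not support that. What remains is the between-condition gene lists, which do not cancel, and the attribution of an interaction to hormone, which assumes a common response to vehicle and culture.

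A second reply is that a vehicle-matched contrast already exists: DMSO alone against continued E/P, at the same age and after the same history. This also stands, for withdrawal. A reader might take the withdrawal comparison to lack a control as well, but the culture is in the design and only the stated ANOVA leaves it out. It does not recover the three-day exposure effect.

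Third, untreated could mean only without hormone, so the baseline might contain DMSO. The wording permits that but does not say it, and a vehicle-containing baseline taken before exposure would still leave T1 in the contrast. The steroid-free period ("5 days before hormone exposure, LCLs will be cultured in a sex steroid-free growth medium") standardises the starting state and is not a concurrent control.

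Finally, the 71% figure reflects the largest shift and the most lines considered. It is not evidence of how many genes would be misassigned here.

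**Conclusion.** The point holds for the exposure contrast. As written, exposure minus untreated is hormone plus DMSO plus three days of culture, and the hormone part is not estimable from the three ANOVA levels or from all four collected conditions. This rests on reading the baseline as vehicle-free and taken before exposure, which is the natural reading but is inferred.

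The effect is limited to the exposure gene lists, the pathway and qRT-PCR results that follow from them, and the interpretation of a diagnosis-by-exposure interaction. This is one component among several outcomes; the clinical mood comparison and the power statement in section 10 are unaffected. The size is not known, and the range shown runs from barely above nominal to a majority of experiments. The change is worth making because the misattribution follows from carrying out the plan as written, and the remedy is small.

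**What to change.** In the paragraph on cell culture and collection, specify for each line a parallel culture in DMSO alone for the same three days, harvested with the E/P culture. It can replace the untreated baseline, or be added to it if untouched basal expression is wanted for the replication in Aim 2b. State whether the baseline medium contains vehicle.

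In the analysis paragraphs:

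- Make the three-day DMSO culture the reference for hormone exposure in the differential-expression, ANOVA, pathway and qRT-PCR comparisons.
- Test withdrawal as DMSO alone against continued E/P at day 6, and add continued E/P to the ANOVA factor. This part is needed because the new day-3 reference does not remove elapsed time from a comparison with the day-6 withdrawal culture.

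The swap adds no culture, but basal expression is then read in vehicle. Whether the previously observed basal differences were measured that way is not stated, so this may matter for Aim 2b. Adding the culture costs one more culture and library per line. Neither option needs more participants or any change to clinical procedures.
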